### 9.2.1.3. Follow-up

Individuals will be followed-up from the day after Time 0 (i.e., day 1) until the first occurrence of 1 of the following:

- The date of an occurrence of the study outcome under evaluation (each outcome will be evaluated separately, and individuals may have different follow-up times for each outcome)
- Censoring at any of the following events:
  - End of the study period (i.e., end of available study data)
  - Loss to follow-up in the data source
  - Deviation from the treatment strategy defined on Time 0 for the primary analysis
    - Finerenone-exposed individuals discontinuing use of finerenone for reasons other than hyperkalaemia (pausing or discontinuing treatment for elevated serum potassium is consistent with treatment dose adjustment strategies [13]) or ESKD (discontinuing treatment for ESKD is consistent with treatment recommendations) [22]
    - Nonusers initiating finerenone

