- A3: > 300, severely increased
- Unknown, for individuals without baseline UACR values

The UACR categories will be identified if available, as they provide additional information regarding cardiovascular disease risk and kidney prognosis [5], but they will be defined as a separate variable from CKD stage; for CKD staging, only eGFR values or diagnosis codes will be used.

The most recent UACR value on or during the 365 days before Time 0 will be used as the baseline UACR value for the UACR-specific analysis set. Additional UACR laboratory values occurring during follow-up will be identified to define UACR-based outcomes.

Additionally, diagnoses of proteinuria and nephrotic syndrome will be identified. ICD-10-CM diagnosis codes for proteinuria do not indicate stage, and there may be considerable overlap between diagnosis-based measures and the UACR measurements for those with available laboratory values; however, diagnosis-based measures may be used in combination with laboratory test–based measures.

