## 9.3.3.2.4. Change in UACR

In clinical trials, finerenone has been demonstrated to have beneficial effects on UACR [31,32], and UACR declines of 30% have been associated with favourable long-term kidney outcomes [32-34]. Guidelines for CKD management in patients with T2D recommend targeting 30% reductions in UACR to prevent CKD progression [35]. In this study, the secondary analysis will evaluate the time to a 30% decrease from baseline UACR values during follow-up; additional thresholds (e.g., 50% decline, 70% decline) may also be considered. This analysis will be performed in an analysis set of those with available baseline UACR laboratory values, and recorded UACR laboratory values during follow-up will be used to define the outcomes of interest.

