#### 9.3.4. Covariate definitions

Covariates include risk factors for renal progression [39,40], cardiovascular outcomes [41,42], or hyperkalaemia [43-45]. Variables potentially associated with the use or non-use of finerenone and the outcomes of interest—e.g., concomitant medications, comorbidities—will be identified for all cohort members before or on Time 0 using diagnosis, procedure, or medication information available in the data source. A detailed description of definitions and code lists for all covariates that will be used in the data source will be specified in the SAP. Covariates will be defined using ICD-10-CM diagnosis codes, laboratory records, procedure coding, or medication coding, as appropriate for each variable.

The following demographic characteristics will be evaluated as of Time 0:

- Age
- Sex
- Calendar year of Time 0
- Race and/or ethnicity (as available in the data)
- Socioeconomic status (as available in the data)
- US geographic region
- Insurance plan type

The following clinical characteristics of patients will be defined using the 365 days before and including Time 0, except where specified otherwise:

- Markers of T2D severity (as available in the data source) and components of the Diabetes Severity Complications Index [46,47] not listed elsewhere
  - Duration of T2D (in all available lookback, as available in the data source)
  - Insulin use
  - Haemoglobin A1c (glycated haemoglobin) (HbA1c) (most recent recorded laboratory value in the 183 days before and closest to Time 0, if available)
  - Hyperosmolar hyperglycaemic state
  - Ketoacidosis

- Lower limb amputations (all available lookback, as available in the data source)
- Neuropathy
- Retinopathy
- Markers of kidney dysfunction severity
  - Duration of CKD (all available lookback, as available in the data source)
  - CKD stage, defined based on eGFR, or stage-specific diagnosis codes (using all available lookback) (Section 9.3.1)
  - Albuminuria stage defined based on UACR values (Section 9.3.1)
  - Proteinuria, defined based on diagnosis codes (Section 9.3.1)
  - Nephrotic syndrome, based on diagnosis codes (Section 9.3.1)
  - Glomerulonephritis
  - Renovascular disease
  - Polycystic kidney disease
  - Autoimmune disease
  - Gout/hyperuricaemia
  - Hospitalisation episodes for acute kidney injury

The following comorbidities will be defined using all available lookback before and including Time 0:

- Cardiovascular comorbidities
  - Acute myocardial infarction

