  - Atherosclerosis
  - Atrial fibrillation
  - Cerebrovascular disease (stroke or transient ischaemic attack)
  - Congestive heart failure
  - Hypercholesterolaemia
  - Hyperlipidemia
  - Hypertension
  - Peripheral vascular disease
  - Unstable angina
- Other components of the Charlson Comorbidity Index or similar comorbidity score [48,49] (as single entities, not listed elsewhere)
  - Anaemia
  - Chronic obstructive pulmonary disease
  - Congestive heart failure
  - Dementia

- Human immunodeficiency virus
- Liver disease
- Malignancy other than kidney cancer or nonmelanoma skin cancer
- Paralysis
- Other comorbidities
  - Coronavirus disease 2019 (COVID-19) diagnosis
  - Hyperkalaemia (history of hyperkalaemia, more than 90 days before Time 0)
  - Osteoporosis
  - Pneumonia

The following lifestyle cardiovascular factors will be defined, as available in the data:

- Body mass index or evidence of obesity
- Smoking status
- Alcohol abuse

The following healthcare utilisation measures will be identified in the 365 days before and including Time 0 to characterise patients' healthcare access, healthcare-seeking behaviour, and indicators of disease state at the time of index medication initiation:

- Healthcare utilisation
  - Hospital visits and hospital admissions
  - Emergency department visits
  - Long-term care or skilled nursing facility residence
  - Number of eGFR laboratory tests performed
  - Number of serum potassium laboratory tests performed
- Preventive health services
  - Influenza vaccination
  - Pneumococcal vaccination
  - COVID-19 vaccination
  - Bone mineral density test
  - Screening mammogram
  - Other cancer screening
- Frailty indicators [50]
  - Arthritis
  - Bladder dysfunction
  - Dementia
  - Psychiatric illness
  - Weakness
  - Vertigo

The following comedications will be identified in the 183 days before and including Time 0 to characterise individuals' recent treatments and indicators of disease state at the time of index medication initiation:

- Medications for T2D
  - Alpha glucosidase inhibitors
  - Dipeptidyl peptidase-4 inhibitors (DPP-4i)
  - GLP-1 RA
  - Meglitinides
  - Metformin
  - SGLT2i
  - Sulfonamides
  - Sulfonylureas
  - Thiazolidinediones
  - Insulin
- Cardiovascular medications
  - Angiotensin-converting enzyme inhibitors/angiotensin receptor blockers (ACEi/ARBs)
  - Aldosterone receptor blockers
  - Angiotensin receptor-neprilysin inhibitor
  - Anticoagulants

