### 9.7.5.2. Change in UACR values over time

The analysis of change in UACR values over time will be performed in an analysis set restricted to those with available baseline UACR values (Section 9.3.3.2.4). Recorded UACR values during follow-up will be identified and used to estimate change in UACR values from baseline at 4 months and 12 months after the Time 0 with pattern-mixture models [61]. The factors considered as censoring criteria for the other, time-to-event outcomes will be used to define loss-to-follow-up for these analyses.

Descriptive analyses of UACR over time at 4 months and 12 months will be performed in each treatment group. Comparisons between groups may be considered, if feasible, based on descriptive analyses of UACR testing frequency between treatment groups (Section 9.7.4.3; further details to be provided in the SAP).

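### The UACR baseline may be up to 365 days old, so a fall before Time 0 can count as change after it, and the protocol's planned checks do not look at sample age

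*Protocol*

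**What the plan says.** Section 9.3.1 defines the baseline for the UACR-specific analysis set: "The most recent UACR value on or during the 365 days before Time 0 will be used as the baseline UACR value". Two objectives use it:

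- The secondary outcome in section 9.3.3.2.4: "the secondary analysis will evaluate the time to a 30% decrease from baseline UACR values during follow-up".
- The exploratory outcome in section 9.7.5.2, where follow-up values are "used to estimate change in UACR values from baseline at 4 months and 12 months after the Time 0 with pattern-mixture models".

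Follow-up starts the day after Time 0 (section 9.2.1.3). Entry to the set needs only a baseline value: "This analysis will be performed in an analysis set of those with available baseline UACR laboratory values".

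On background drugs, section 9.3.4 states: "The following comedications will be identified in the 183 days before and including Time 0". The lists that follow include SGLT2i, GLP-1 RA, ACEi/ARB and other MRAs, and section 9.7.2 applies the propensity weights to all analyses. Sections 9.7.4.3 and 9.7.5.2 make comparisons between groups conditional on feasibility, judged by how often UACR is tested in each group. Incidence rates, cumulative incidence plots and the 4- and 12-month descriptions are planned for each group in any case.

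**The concern.** A one-year look-back suits a severity covariate such as albuminuria stage. Here the same value is also the reference point of a change outcome, so its age enters the result directly.

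If UACR fell between the sample and Time 0 and stayed down, the first follow-up test records the fall as an event, or as part of the 4-month change. It is then credited to finerenone or to non-use, although it came before either. Section 7 lists ACEi/ARB and SGLT2i among the therapies used in this population, so another drug may well have been started in that gap.

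The covariates cannot detect this. Two patients who both count as SGLT2i users in the 183-day window may differ in that one has a pre-drug baseline and the other an on-drug baseline. Balancing use need not balance that timing. Sample age may also differ by arm: section 9.2.1.1 allows several comparator Time 0s per person, so one old sample can serve several records, whereas each finerenone user has a single Time 0 at a prescribing decision.

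**Working it through.** **Maximum span between samples.** The protocol gives no span, sample size or precision for the UACR outcomes, so there is no stated figure to reproduce. Inputs: look-back of 365 days (section 9.3.1); time points of 4 and 12 months after Time 0 (section 9.7.5.2); 1 month = 365.25/12 days. Maximum span = look-back + time point; share before Time 0 = look-back / span.

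| Look-back | 4-month change: maximum span (share before Time 0) | 12-month change: maximum span (share before Time 0) |
|---|---|---|
| 365 days (plan) | 365 + 121.75 = 486.75 days = 16.0 months (75%) | 365 + 365.25 = 730.25 days = 24.0 months (50%) |
| 183 days | 10.0 months (60%) | 18.0 months (33%) |
| 90 days | 7.0 months (42.5%) | 15.0 months (20%) |

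The last two rows use windows that the protocol applies elsewhere: 183 days for HbA1c and comedications (section 9.3.4), 90 days for the eGFR and potassium exclusions (section 9.2.1.2). All spans are upper bounds.

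**What the safeguards observe.** The 183-day covariates record use, not the start date relative to the UACR sample. The feasibility check observes testing frequency. Neither contains the days from sample to Time 0, nor a drug start within those days. The protocol plans no shorter-window sensitivity analysis for UACR.

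**Illustration of a fall before Time 0.** Every input here is an assumption. Within-person UACR is log-normal with a coefficient of variation (CV) of 30 to 50%, and a drug started between sample and Time 0 lowers UACR by 20 or 30%. Finerenone has no effect. The SD of a log difference is s = √2 × √ln(1 + CV²). The chance that the first follow-up value is at least 30% below baseline is Φ[(ln 0.7 − ln(1 − fall)) / s].

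| CV | No fall | 20% fall before Time 0 | 30% fall before Time 0 |
|---|---|---|---|
| 30% | 0.20 | 0.37 | 0.50 |
| 40% | 0.26 | 0.40 | 0.50 |
| 50% | 0.30 | 0.42 | 0.50 |

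For an affected record, the chance of an apparent event at the first test thus rises from 20–30% to 37–50%. If such records were 10 percentage points more common in one arm, that arm's proportion would rise by 0.10 × (0.42 − 0.30) = 1.2 points at the low end, and by 0.10 × (0.50 − 0.195) = 3.1 points at the high end (0.195 is the unrounded 0.20). The 10-point imbalance is hypothetical and could favour either arm.

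**The case against.** The strongest case against is that this is a defensible choice of window on outcomes that are largely descriptive. Much of that stands.

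- A reader might infer that 365 days breaks the protocol's own laboratory standard. It does not. The 90-day rules are exclusion screens, 365 days is the default for clinical characteristics in section 9.3.4, and CKD stage uses all available look-back. HbA1c is the one laboratory covariate there with a shorter window: "most recent recorded laboratory value in the 183 days before and closest to Time 0, if available".
- Taking the most recent value makes the sample as fresh as the data allow. Section 9.2.1.1 assumes at least one physician visit a year, which makes a one-year look-back reasonable.
- A reader might infer that the finerenone arm is biased in a known direction. The documents do not support that. A start soon after a fresh test leaves less time for an intervening drug, while a start after a step-up of other therapy makes one more likely. The net effect is unknown. The protocol cites a UACR effect for finerenone only; the effect of other drugs is assumed here.
- Weighting on comedication class and albuminuria stage removes part of any imbalance. What remains is start timing among users and sample age.
- A reader might conclude that 90 days should become the main window. That would cost sample, may keep comparators who were tested for cause, and may increase regression to the mean where a high recent value prompted treatment. Dropping recent starters of other drugs from the main analysis would also narrow a set meant to reflect on-label use.
- Sample age as a covariate, and a sensitivity analysis, could be set in the SAP, which is not at hand.

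The objection does not remove the mechanism. The baseline rule is fixed in the protocol, and comedication weighting cannot correct each group's own change, which is the exploratory objective itself.

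**Conclusion.** The point holds as a limitation of the secondary and exploratory UACR outcomes that is cheap to reduce. The maximum spans of about 16 and 24 months follow directly from sections 9.3.1 and 9.7.5.2. How often they are approached is unknown, because the documents give no distribution of sample age. A lasting fall between the sample and Time 0 is counted as change after Time 0, and neither the comedication covariates nor the testing-frequency check would reveal it.

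The shift of 1.2 to 3.1 percentage points is an illustration under assumed variability, drug effect and imbalance; it is not an estimate for this study. The documents establish neither the size nor the direction of a bias between arms, and they give no ground for calling the 365-day window an error. The primary cardiovascular analysis is unaffected.

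**What to change.** Keep the 365-day baseline for the main UACR analysis. For the UACR analysis set only:

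1. Add to the propensity model (a) days from the baseline sample to Time 0 and (b) an indicator for a first SGLT2i, ACEi/ARB, GLP-1 RA or MRA (other than finerenone) record between the sample and Time 0. Both are known at Time 0.
2. Report both by arm beside the testing-frequency check in section 9.7.4.3.
3. Add a sensitivity analysis restricted to a baseline within 183 or 90 days that excludes records with such an intervening start. This also addresses the within-group change, which item 1 does not correct.

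The cost is slightly more analysis work on data already held, and a smaller, possibly more selected set in the sensitivity analysis alone. One caution: only 365 days of enrolment before Time 0 are guaranteed (section 9.2.1.2), so for an old sample there may be little earlier history to show that a drug record is truly the first. The indicator should use all available look-back. The primary analysis does not change.

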### 9.3.2. Exposure definition

Finerenone exposure will be identified from provider prescription records in EHRs or pharmacy dispensing records from pharmacy claims, as available. The first observed record for a finerenone prescription or dispensing during the study period will be considered the date of finerenone initiation. If any previous finerenone use is observed at any point before the finerenone prescription (using all available lookback data per person), the prescription will not be considered an incident prescription (i.e., each individual will contribute only 1 potential finerenone Time 0 to the study). Treatment discontinuation will be estimated from prescribing and pharmacy dispensing records from EHRs and/or claims data.

Combinations of prescribing and dispensing records may be used to define treatment periods, and discontinuation dates may be estimated from the available information in the database. Various grace periods and different sets of assumptions may be considered to define exposure periods based on the availability of different types of prescription data (i.e., EHR-based written prescription records and claims-based pharmacy dispensing) and will be described in the SAP.

### 9.3.2.1. Finerenone initiation treatment strategy

The treatment strategy evaluated by this study will be initiation and continuing use of finerenone. Deviation from the treatment strategy will be defined as discontinuation of finerenone for reasons other than elevated potassium or ESKD, which is consistent with the label and treatment recommendations.

Finerenone initiation will be defined as the first observed finerenone prescription during the study period. For the primary analysis, finerenone initiators will be permitted to up-titrate or down-titrate dosages while remaining adherent to the treatment strategy. Guidelines allow for pauses in finerenone treatment after the occurrence of elevated serum potassium [13]; thus, gaps in use or discontinuation of finerenone after an elevated serum potassium laboratory measurement or diagnosis of hyperkalaemia will not be considered deviation from the

treatment strategy. Additionally, the European Union (EU) label explicitly calls for discontinuation of finerenone in ESKD [22]; thus, discontinuation for ESKD will not be considered deviation from the treatment strategy.

### 9.3.2.2. Comparator, non-use treatment strategy

The treatment strategy for the comparator group will be not initiating finerenone. For the comparator group, previous use of finerenone at any point before Time 0 will be evaluated using all available data to ensure that the individuals are free of any previous use of finerenone. The non-use treatment strategy will require individuals to be free of finerenone use; individuals will be considered to have deviated from the treatment strategy if they initiate finerenone use during follow-up.

### 9.3.2.3. Finerenone initiation and titration treatment strategy

As a secondary analysis, an additional treatment strategy will be evaluated in which patients are required to initiate finerenone and up-titrate to the target daily dosage of 20 mg, per the approved US label [13]. Patients using this treatment strategy will be identified at finerenone initiation (either at 10 mg or 20 mg). Among those who initiate finerenone at 10 mg per day, failure to up-titrate to 20 mg per day by 10 weeks after initiation (more than twice the recommended 4-week period) will be considered deviation from the treatment strategy (unless serum potassium levels are greater than 4.8 mEq/L, as the US label instructs maintaining the 10-mg daily dosage). Those who initiate finerenone at 20 mg per day will be considered adherent to the treatment strategy. Subsequent down-titration back to 10 mg will be allowed, consistent with allowed dose adjustments [13].

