- A diagnosis of adrenal insufficiency (i.e., congenital adrenogenital disorders of enzyme deficiency, primary or secondary adrenocortical insufficiency, Addison's disease, pituitary neoplasm, or other pituitary disorder [19]) at any time on or before Time 0 (days [-all available, 0]), as finerenone is contraindicated in individuals with adrenal insufficiency [13]
- Evidence of hepatic impairment, including hepatic failure, fibrosis, cirrhosis, or chronic hepatitis, at any time on or before Time 0 (days [-all available, 0]), as treatment with finerenone is to be avoided in individuals with severe liver impairment [13]
- An eGFR measurement < 25 mL/min/1.73 m^2 on or in the 90 days before Time 0 (days [-90, 0]), as finerenone is not recommended to be initiated in individuals with eGFR < 25 mL/min/1.73 m^2 [13]
- Evidence of recent increased serum potassium or hyperkalaemia, as finerenone is not recommended for initiation in individuals with elevated serum potassium [13], identified as either of the following:
  - A serum potassium test result > 5.0 mEq/L on or in the 90 days before Time 0 (days [-90, 0])
  - A diagnosis code indicating hyperkalaemia on or in the 90 days before Time 0 (days [-90, 0])
- Use of a strong CYP3A4 inhibitor on or in the 183 days before Time 0 (days [-183, 0]), as finerenone is a CYP3A4 substrate and is contraindicated in users of strong CYP3A4 inhibitors [13]. Examples include the following [20,21]:
  - Cobicistat
  - Itraconazole

- Ketoconazole
- Posaconazole
- Ritonavir
- Telithromycin
- Troleandomycin
- Voriconazole
- Evidence of pregnancy measured on or in the 40 weeks before Time 0, as clinical practice guidelines discourage the use of finerenone during pregnancy [16]

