### 9.4. Data sources

This study will be conducted using existing healthcare data from the US. Considered data sources include the HealthVerity® Chronic Kidney Disease Masterset. This data source includes closed administrative health insurance enrolment, medical claims, and pharmacy claims data supplemented with laboratory test results, electronic medical record information, and mortality records. The Masterset contains information on over 10 million unique patients with evidence of CKD in the US with commercial, Medicare Advantage, or Medicaid insurance coverage.

Additional data sources may be considered to increase the sample size or representativeness of the study sample. If multiple data sources are used, meta-analytic methods may be considered, as appropriate, to generate summary estimates across data sources. Should additional data sources be added, the data source will be recorded and described in an update of the protocol, and a data source–specific SAP will be prepared to describe and document any data source–specific adaptations.

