### 9.7.3. Primary effectiveness analyses

The primary composite cardiovascular outcome will be evaluated in an analytic subset after the application of outcome-specific exclusion criteria to ensure analysis of new-onset disease (Section 9.3.3.1) using an outcome-specific propensity score model; the assessment of weighted covariate balance (Section 9.7.2) in this analytic subset will be evaluated.

To account for baseline confounding, the propensity score–based weights will be applied to the cohort to balance characteristics across treatment groups, and analyses will be performed in the weighted cohort [57]. Because the 2 treatment groups will be subject to censoring after follow-up begins, selection bias may be introduced if individuals are censored differentially between treatment groups. To account for this potential bias, time period–specific inverse probability of censoring (IPC) weights will be estimated with logistic regression with censoring status as the dependent variable and updated time-varying characteristics as the independent variables. A full description of included variables and operationalisations will be provided in the SAP. The IPC weights will also be applied to the analysis [57]; the product of the baseline sIPT and time period–specific IPC weights will be applied during each time period of follow-up to account for both baseline confounding and selection bias in follow-up.

The incidence rates and 95% CIs of the composite cardiovascular outcome across all of follow-up will be estimated in the weighted cohort. A weighted cumulative incidence plot will be generated by treatment group using the cumulative incidence function estimator to visualise the occurrence of outcome events by follow-up time, accounting for censoring criteria and the competing risk of death [58]. This approach will estimate the "total effect" of finerenone on the outcome events or the cause-specific cumulative incidence [59]. Time since Time 0 (i.e., treatment initiation) will be the time scale.

As a summary of the relative difference in outcome incidence between the treatment groups, a HR and 95% CI will be estimated with weighted Cox proportional hazards ratios. The 95% CI will be estimated with robust sandwich estimators to account for the sIPT and IPC weighting and for the possibility of a single individual contributing multiple observations with different Time 0s.

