### 9.7.8. Secondary treatment strategy analysis

A secondary analysis will evaluate outcomes using an alternative treatment strategy, requiring uptitration of the daily finerenone dose to 20 mg according to the approved US label (Section 9.3.2.3). This strategy will use methods similar to those for the primary analyses, but the censoring criteria will also include deviation from the new strategy (i.e., failure to titrate by week 10). These analyses will begin with the same study population as that from the primary analysis; thus, the same propensity scores and baseline variables will be used, but new IPC weights will be calculated due to the difference in censoring criteria.

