#### 9.9. Limitations of the research methods

This study will use existing healthcare data. As with all studies based in existing healthcare data sources, the data are generated for healthcare delivery rather than research; thus, missing data or misclassification of study variables is possible.

Written prescription or dispensing data may not reflect actual exposure or nonexposure to finerenone. A prescription issued or a prescription dispensed reflects the intent to use a drug, not actual patient use. Dosage, duration of use, and treatment changes will be estimated from the data; however, not all patient behaviours may be accurately recorded in the data, resulting in potential misclassification of finerenone use, discontinuation date, or dosage.

CKD will be defined using laboratory values (where available) and diagnosis coding. This approach may introduce heterogeneity in the evaluation of CKD severity across study participants. Additionally, formulas for estimating eGFR may vary across time, geographies, and racial and/or ethnic groups. This study will use a standard single equation, CKD-EPI 2021, to estimate eGFR where possible. However, in the absence of complete laboratory records, diagnosis coding will be used, which may lack the granularity of laboratory-based measures.

Cohort entry is defined by meeting electronic algorithms for both T2D and CKD using data available in the data source during the study period. Thus, the original dates of CKD and T2D onset may not be known for each individual. Additional measures of T2D and CKD disease severity will be included as covariates, but duration of illness cannot be considered.

Moreover, specific ordering of the onset of CKD and T2D will not be required. Individuals with T2D who develop CKD may have different treatment patterns and characteristics than those with CKD who develop T2D, but both groups will be included in the present study.

Outcomes will be identified using all relevant diagnosis information using validated algorithms, where available; however, misclassification is possible.

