To optimise internal validity, this study will assess patients who have been or who could have been prescribed finerenone according to the approved label in the US. Some of these eligibility criteria based on the approved label or treatment recommendations are intended to improve comparability of treated and untreated groups (e.g., exclusion of those with recent hyperkalaemia), thus avoiding comparison of treated individuals with untreated individuals whose clinical state makes them unlikely to be treated and more likely to experience negative outcomes. These criteria are primarily intended to impact the untreated comparison group, but they are also likely to exclude a small number of treated individuals. Consequently, this approach may impact the representativeness of the study results. The study results will be representative of patients prescribed finerenone according to the approved label in the US, but results need to be interpreted with care beyond the labelled indication of finerenone in the US.

A secondary objective of this study will assess the effectiveness of initiating finerenone and titrating dosage according to the approved label by estimating the risk of a composite cardiovascular outcome (i.e., first occurrence of fatal or nonfatal AMI or hospitalisation for heart failure) in patients with CKD and T2D initiating finerenone and uptitrating to 20 mg (when recommended) compared with that in patients with CKD and T2D not using finerenone. Patients in the finerenone group will therefore be censored if they do not seem to follow the titration recommendation from the US label. However, in the control group (no

finerenone use), no such censoring will be possible because these patients do not use finerenone.

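### In the secondary titration analysis, 9.3.2.3 excuses staying on 10 mg only by a potassium value; it should also accept a hyperkalaemia diagnosis, as 9.3.2.1 does

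*Protocol*

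**What the plan says.** Protocol 9.3.2.3 defines a secondary strategy of starting finerenone and reaching 20 mg per day. Someone who starts on 10 mg and has not moved to 20 mg within 10 weeks has deviated, "unless serum potassium levels are greater than 4.8 mEq/L, as the US label instructs maintaining the 10-mg daily dosage". No other reason for staying on 10 mg is given. Section 9.7.8 turns this into censoring: "the censoring criteria will also include deviation from the new strategy (i.e., failure to titrate by week 10".

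Elsewhere the protocol identifies raised potassium from two sources. In the primary strategy (9.3.2.1), gaps or discontinuation "after an elevated serum potassium laboratory measurement or diagnosis of hyperkalaemia" are not deviation. At entry (9.2.1.2), patients are excluded for "A serum potassium test result > 5.0 mEq/L on or in the 90 days before Time 0" or, as a separate criterion over the same window, for a hyperkalaemia code.

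Section 9.4 describes the source as "pharmacy claims data supplemented with laboratory test results, electronic medical record information, and mortality records". Section 9.9, writing about the classification of CKD, says that "in the absence of complete laboratory records, diagnosis coding will be used". On the comparator side, 9.9 notes for the titration rule that "no such censoring will be possible because these patients do not use finerenone".

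**The concern.** The secondary objective in 8.2 is uptitration when it is recommended. Staying on 10 mg because potassium is high is therefore adherence. The rule can recognise that adherence only through a potassium result in the data. Without one, a correctly managed patient looks the same as one who simply was not titrated, and both are censored at week 10. For those patients the analysis drifts from uptitration when recommended towards having reached 20 mg.

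The patients lost this way are finerenone users with higher potassium, and comparable nonusers stay in follow-up. The plausible direction is in favour of titrated finerenone, chiefly for hyperkalaemia if that outcome is analysed under this strategy. Section 8.2 speaks of outcomes of interest in general. The limitations text in 9.9 describes the objective by the cardiovascular composite, for which no material effect is claimed here.

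**Working it through.** The protocol gives no figure for this point. Its study sizes in 9.5 concern the primary outcome and do not bear on it. The one number in the rule that can be checked is consistent: 10 weeks / 4 weeks = 2.5, which is more than twice the recommended period.

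**Step 1. The three rules side by side**

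| Section | Purpose | Laboratory value accepted | Diagnosis accepted |
|---|---|---|---|
| 9.2.1.2 | exclusion at Time 0 | above 5.0 mEq/L, days [-90, 0] | yes, same window |
| 9.3.2.1 | excuse for a gap or stop, primary strategy | elevated potassium | yes |
| 9.3.2.3 | excuse for staying on 10 mg, titration strategy | above 4.8 mEq/L | not named |

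**Step 2. One patient under both strategies.** A patient starts on 10 mg, receives an outpatient hyperkalaemia code in week 5, pauses treatment, and has no linked potassium result. Under 9.3.2.1 the pause is not deviation. Under 9.3.2.3, read literally, the patient is not on 20 mg at week 10, has no value above 4.8 mEq/L, and is censored under 9.7.8. The entry rule removes anyone coded in the 90 days up to and including Time 0, so a code found between initiation and week 10 has no coded episode in the 90 days before it to carry over from.

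**Step 3. What a diagnosis alternative can recover.** Entry excludes only values above 5.0 mEq/L. A patient can therefore start between 4.8 and 5.0, be correctly kept on 10 mg, and never carry a hyperkalaemia code. For the hyperkalaemia outcome, 9.3.3.2.5 already counts a hospital or emergency code as the event, so the alternative adds only outpatient codes there.

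**Step 4. Illustration with assumed inputs.** Take 1,000 patients not on 20 mg at week 10 whose true potassium is above 4.8 mEq/L. Let L be the share with a result in the data that shows this, and d the share of the others who carry a hyperkalaemia code. Neither is in the protocol. The ranges assumed are L = 0.3 to 0.9 and d = 0.1 to 0.3.

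- Wrongly censored under the present rule: 1,000 × (1 − L)
- Recovered by a diagnosis: 1,000 × (1 − L) × d
- Still wrongly censored: 1,000 × (1 − L) × (1 − d)

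| L | d | Wrongly censored now | Recovered | Remaining |
|---|---|---|---|---|
| 0.9 | 0.1 | 100 | 10 | 90 |
| 0.9 | 0.3 | 100 | 30 | 70 |
| 0.3 | 0.1 | 700 | 70 | 630 |
| 0.3 | 0.3 | 700 | 210 | 490 |
| 1.0 | any | 0 | 0 | 0 |

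The share recovered equals d whatever L is. The table shows that the remedy is partial; it does not estimate bias in any hazard ratio.

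**The case against.** The best defence is that 9.3.2.3 states a clinical rule and that its operation belongs to the SAP. Section 9.10.2 allows diagnosis records to stand in for a missing laboratory value for some variables, and 9.3.2.3 does not say that a patient without a result counts as below 4.8. Section 9.7.8 builds on the primary methods, so the primary excuse could be read as carrying over. This has some force: the SAP may read the rule generously. But the wording in 9.10.2 is permissive, its example is CKD stage, and 9.3.2.3 names a single excuse where its sister section names two. The present text does not settle the question, and one phrase would.

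It is also fair that a hyperkalaemia code is no proxy for 4.8 mEq/L, and that holding a dose is a different decision from pausing. That limits what the fix achieves but does not argue against making it.

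A reader might infer that the protocol has no defence against this bias. It does not go that far. Section 9.7.1 already reports reasons for censoring, and 9.9 discloses selection bias from titration censoring and the residue left by unmeasured characteristics. The censoring weights use "censoring status as the dependent variable and updated time-varying characteristics as the independent variables", with the variables left to the SAP. The covariates in 9.3.4 include usable proxies, such as history of hyperkalaemia, number of potassium tests, CKD stage and potassium binders. The weights can reduce the bias, although they cannot use a potassium value that was never recorded.

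A reader might also conclude that a version restricted to laboratory-linked patients is required. It is not. Such a set would be selected on having been tested, and a test in the year before Time 0 does not ensure one between initiation and week 10, which is where the gap lies.

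**Conclusion.** The point holds as a narrow inconsistency in a stated rule. Section 9.3.2.3 accepts one kind of evidence for a label-consistent reason to stay on 10 mg, where 9.3.2.1 and 9.2.1.2 accept two, in a source whose laboratory data are supplementary. Followed literally, it censors some patients who are following the label.

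The size cannot be determined from the protocol. It depends on laboratory coverage and coding practice, neither of which is given, and it vanishes with full capture. The direction, favouring titrated finerenone on hyperkalaemia, is plausible but not shown. It would be tempting to read this as a threat to the study's main result. The documents do not support that: the week-10 rule applies only to the secondary titration analysis, and the primary strategy already accepts a diagnosis.

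**What to change.** In 9.3.2.3, excuse failure to up-titrate when serum potassium is above 4.8 mEq/L or when a hyperkalaemia diagnosis is recorded between initiation and week 10, in line with 9.3.2.1. In 9.7.1, for week-10 titration censoring, split the planned count by whether a potassium result was available between initiation and week 10. That split shows how many censored patients could not have been recognised as adherent from laboratory data.

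The cost is one phrase and two counts. The 4.8 mEq/L threshold, the 10-week limit, the study size and the analysis population all stay as they are. The small downside is that a code is coarser than the threshold: it will miss mild elevations between 4.8 and 5.0 and, for the hyperkalaemia outcome, adds only outpatient codes. A laboratory-linked sensitivity version may be added if the sponsor wishes, but the fix does not depend on it.
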